1.0 Objectives

- **1.1 Primary**: Compare the response rates of two schedules of decitabine in patients with AML 60 and older than 60 and/or unfit for standard cytotoxic chemotherapy.
- **1.2 Secondary**: Compare response durations, survivals and side effects of the two schedules.
- **1.3 Tertiary**: To examine the correlation of a number of biological and pharmacodynamics correlates with response to therapy including global and gene-specific methylation, specific somatic gene mutations, micro-RNA, and immune effector function

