d. A minimum of 1 full course (or 4 weeks from the start of therapy) will be required for a patient to be considered as having received an adequate trial to evaluate efficacy. All patients receiving at least one dose of decitabine will be considered evaluable for toxicity. Patients achieving a partial response or with stable disease may continue on therapy until definite evidence of disease progression.

e. Patients who achieve CR or CRi may be treated with additional courses of decitabine every 4-8 weeks or longer if approved by the PI. The dose of decitabine can be adjusted down by one dose level for toxicity (see above). Patients may be taken off study or treated on other programs (e.g. bone marrow transplantation) if this is judged more appropriate for their therapy and overall outcome. Delays of more than 8 weeks to subsequent course may be allowed if determined by the investigatory to be in the best interests of the patient after discussion with the PI and the discussion documented in the patient's medical record. Abnormalities in chemistries including BUN, LDH (lactic dehydrogenase), alkaline phosphatase, magnesium, glucose, phosphorus, calcium and electrolytes will not be reported as adverse events. These are indications of disease process and not of toxicity, therefore clinically insignificant. Delayed recovery in patients post CR is common in MDS and AML not associated with significant clinical complications such as bleeding or infections. Therefore, delayed myelosuppression after a course in CR will be

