11.3 Study Design

A maximum of 100 patients will be adaptively randomized into two treatment groups:

Arm A: Decitabine 20mg/m2 IV daily for 5 days

Arm B: Decitabine 20mg/m2 IV daily for 10 days

Patients will be assigned to receive different schedules of Decitabine, using an adaptive procedure that bases assignment probabilities on observed results in preceding patients. At first, 20 patients will be assigned to each arm with equal probability. As efficacy data accrues, patient assignment to the two arms will become unbalanced in favor of the one that has the higher complete response rate (RR). The RR for both arms will be estimated with a 95% CI (similar to Bayesian highest posterior density interval).⁴⁹

Based on previous studies, we expect a RR of about 30% in both arms. Therefore, we assume RR has a prior Beta distribution (0.6, 1.4) with mean 0.3. Let RRa and RRb denote the response rates for arm A and arm B, respectively. Beginning with the 21st patient in each arm and for each subsequent patient, we will compare RRa with RRb, incorporating data from all patients with evaluable response. In order to avoid favoring one arm earlier in a large trial, instead of assigning patients with posterior probability (Pa=Pr(RRa>RRb|data) and Pb=1-Pa), we use the following formula to assign patients:

2012-1017 May 24, 2017 Page **23** of **29**

Aa= $\frac{\sqrt{Pa}}{\sqrt{Pa} + \sqrt{Pb}}$, Ab=1-Aa, where Aa is the probability of assigning patients to arm A, Ab is the

probability of assigning patients to arm B, Pa is the posterior probability that arm A is superior to arm B and Pb is the posterior probability that arm B is superior to arm A.

If at any point during the trial Pr(RRa>RRb|data)>0.95(or <0.05) the schedule A(or B) will be selected as superior. If accruing information gives strong evidence that a RR of 30% or greater is unlikely to be true for any one of the treatment arms (Pr(RRa or RRb>0.3|data)<0.05), assignment to that arm will be stopped. If the maximum of 100 patients is enrolled and evaluated and Pr(RRa>RRb|data)>0.9 (or <0.1), we will declare that arm A(or B) has a higher RR rate than arm B (or A). Otherwise, the trial will be inconclusive. We used simulation (5,000 simulations per scenario) to evaluate the performance of the adaptive randomization procedure under several different scenarios (Table 2). Adaptive Randomization version 4.1 has been used for the simulation. Adaptive Randomization version 4.1 has been used for the simulation.

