11.5 Analysis Plan

Data analysis will be performed using SAS or S-plus, as appropriate. All patients will be included in the intent-to-treat analysis for efficacy. Demographic and disease characteristics of the patients at registration will be summarized using descriptive statistics such as mean, standard deviation (SD), median and range. The RR for both arms will be estimated by Bayesian posterior estimates, along with the 95% credible intervals. The posterior probability that one treatment is better than the other will be computed, and the 95% credible interval of the posterior probability will also be estimated. The time-to-event variables will be estimated by Kaplan-Meier method. The survival difference between the two treatment schedules will be compared by Log-rank test. The OS is defined as the time period from the start of treatment till death or last follow-up whichever comes first. Duration of response (DoR) is for the patients who achieve CR or CRi, and it is defined as the time between the date of response confirmed (CR or CRi) and the date of progression or death (whichever occurs first). DoR will be censored on the date of last follow-up.

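### Overall survival is timed from the start of treatment although efficacy is declared intent-to-treat, so a patient assigned but never dosed has no stated time origin

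*Combined protocol and SAP*

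**What the plan says.** Three sentences of section 11.5 (Analysis Plan) bear on the point.

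- Population: "All patients will be included in the intent-to-treat analysis for efficacy".
- Time origin: "The OS is defined as the time period from the start of treatment till death or last follow-up whichever comes first".
- Comparison: "The survival difference between the two treatment schedules will be compared by Log-rank test".

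Survival is a stated secondary objective in section 1.2: "Compare response durations, survivals and side effects of the two schedules". Section 11.3 makes the comparison a randomised one: "A maximum of 100 patients will be adaptively randomized into two treatment groups". Section 11.1 describes the trial as open-label.

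Two sentences in section 5.3(d) define who counts by reference to treatment. One concerns safety only: "All patients receiving at least one dose of decitabine will be considered evaluable for toxicity". The other concerns efficacy: "A minimum of 1 full course (or 4 weeks from the start of therapy) will be required for a patient to be considered" to have had an adequate trial of the drug. Neither gives a rule for the survival analysis of a patient who is assigned but not dosed. An earlier reference date does exist in the plan, because section 11.5 describes baseline at that date: "Demographic and disease characteristics of the patients at registration will be summarized using descriptive statistics".

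**The concern.** An intent-to-treat survival comparison needs a time zero for every randomised patient. Timing from the start of treatment supplies one only for those who start. Someone who dies, deteriorates or declines between assignment and first dose belongs to the randomised comparison but has no survival time under the definition.

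The issue is who enters the log-rank test more than a shift of a few days in the clock. Non-starters are unlikely to be a random sample: early deaths and rapid deterioration are natural reasons for not starting, and section 4.1 admits patients with ECOG performance status up to 3 who are not candidates for intensive chemotherapy. The arm is known when the loss occurs, and one schedule asks for twice as many infusion days as the other, so non-starting could differ between arms. If it did, leaving these patients out would favour the arm that lost more of those with short survival.

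**Working it through.** **No figure to reproduce.** The plan gives no sample size, event target, significance level or power for survival, and no non-start rate. The check is therefore a comparison of the text, followed by an illustration of scale under stated assumptions.

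**Step 1: text.** The population sentence and the origin sentence in 11.5 agree only if every assigned patient starts treatment. No section ensures that. No section gives a fallback origin such as randomisation or registration, or says how an undosed patient is handled in the survival analysis. The one-dose population in 5.3(d) is limited to toxicity. "All patients" in 11.5 is not defined as all randomised or as all treated.

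**Step 2: patients with a defined survival time.** At the maximum of 100 patients, the number with a time origin is 100 × (1 − d), where d is the overall share never dosed. For assumed d of 2%, 5% and 10%, this gives 98, 95 and 90. Timed from randomisation, it is 100 whatever d is.

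**Step 3: effect on power.** By the Schoenfeld formula with 1:1 allocation and two-sided 0.05, power = Φ(½·√D·|ln HR| − 1.96), where D is the number of deaths. Assume HR 0.6 and that every patient analysed dies. With D = 100 this is Φ(5 × 0.511 − 1.96) = Φ(0.594) = 72.4%.

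| Overall share never dosed (assumed) | Deaths counted | Power |
|---|---|---|
| 0% | 100 | 72.4% |
| 2% | 98 | 71.5% |
| 5% | 95 | 70.2% |
| 10% | 90 | 67.8% |

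The loss of power is small.

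**Step 4: bias when there is no true difference.** This is a simulation of 4,000 trials per scenario with 50 patients per arm, exponential survival and a 24-month cut-off. Both arms have the same mixture: a share q with median survival of 1 month (assumed), and the rest with median 7.7 months, the figure that section 2.3 cites from the phase II study of the 5-day schedule. The share q is then retained in both arms, removed from both, or removed from the 10-day arm only. HR is the 10-day arm against the 5-day arm.

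| q (share of an arm) | All retained: HR; rejection | Removed from both: HR; rejection | Removed from one arm: HR; rejection |
|---|---|---|---|
| 2% | 1.00; 6.0% | 1.00; 5.4% | 0.98; 5.4% |
| 5% | 1.00; 5.2% | 1.00; 5.6% | 0.95; 5.7% |
| 10% | 1.00; 5.1% | 1.00; 6.2% | 0.90; 7.7% |

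In the last column q applies to one arm of 50, so the rows correspond on average to 1, 2.5 and 5 patients in the trial.

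The simulation error on a 5% rejection rate is √(0.05 × 0.95 / 4,000) ≈ 0.3 percentage points. The 5.4% and 5.7% lie within the 5.1% to 6.0% seen when nobody is removed. The clearer signal at 2% and 5% is therefore the shift in the hazard ratio, not test size. Only 10% one-sided loss moves the rejection rate visibly.

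Equal arms of 50 are a simplification. Allocation in the trial is adaptive, and Table 2 expects about 40 per arm when both response rates are 30%.

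**The case against.** **The exclusion is inferred.** A reader might conclude that the plan excludes undosed patients, or that the two sentences of 11.5 flatly contradict each other. Neither is supported. No section says such patients are dropped, and the intent-to-treat sentence points towards including them. Both sentences hold if everyone assigned starts. What stands is narrower: the origin is unspecified for these patients, and the definition as written leaves them out.

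**Differential non-starting is not shown.** Under section 5.2 both arms begin with the same drug, daily dose and infusion time, and differ in the number of days. The documents give no refusal or non-start rate, overall or by arm. A reader might infer that the 10-day schedule will provoke more refusals before dose 1. That is possible, but nothing in the plan measures it. Refusals may also live longer than the 1-month median assumed above, which would shrink the bias.

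**The cited early mortality does not size the problem.** Section 2.3 reports 15% dead within 8 weeks in the single-arm 10-day study. It is tempting to treat part of that figure as deaths before dosing. The 30-day figure in the same sentence is counted from the first treatment, and the 8-week figure appears to be as well. Those deaths would then have followed dosing, and pre-dose deaths would come on top of them.

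**Nothing is decided on survival.** Superiority, the stopping of an arm and the final declaration in section 11.3 all rest on response rate. This stands and limits the importance of the point. It does not remove it, because survival between schedules is a stated objective with a named test, and the choice of origin is better fixed before outcomes are known in an unblinded trial.

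**Conclusion.** The concern holds as a mismatch in the text: 11.5 declares intent-to-treat but uses a survival origin that only treated patients have, and no other section closes the gap. Confidence in that is high.

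Confidence in any resulting bias is not. It needs non-starters, with poor prognosis, lost unequally between arms. If 2% to 5% of one arm were lost in this way, the apparent hazard ratio would move from 1.00 to about 0.98 to 0.95, with little visible change in test size. At 10% of one arm it would be about 0.90, with rejection of 7.7%. Balanced loss leaves it near 1.00. These figures rest on assumed non-start rates, an assumed 1-month median for non-starters, exponential survival and equal arms.

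The likely effect is modest and confined to a secondary endpoint. A reader should not infer that the primary comparison is affected. It uses response, not this definition, and duration of response is timed from the response itself. The change is still worth making, because it restores the randomised comparison at little cost.

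**What to change.** In section 11.5, define overall survival as the time from the date of randomisation (arm assignment) to death from any cause, censored at last follow-up for patients not known to have died. State that the intent-to-treat set is every randomised patient, analysed in the assigned arm. Keep survival from first dose, among treated patients, as a sensitivity analysis, and report the number never dosed by arm with reasons.

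In the same edit, reconcile the efficacy condition in section 5.3(d) with the intent-to-treat statement, so that it is clear which analyses, if any, use it.

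Cost: a few sentences, plus two practical requirements. The assignment date must be captured. It is probably available from the trial website (section 11.2) or from registration (section 5.1), but neither section expressly says that it is stored. Undosed patients must also be followed for survival. No change to sample size, randomisation or the primary analysis is needed.

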5.3 Duration of Therapy

In the absence of treatment delays due to clinically significant study drug related adverse events, treatment may continue until one of the following criteria applies:

- Relapsed or clinically significant progressive disease; no response after
 > 3 courses.
 Patients may continue therapy as long as they have stable disease, as long as it is
 determined to be in the best interest of the patient.
- Intercurrent illness that prevents further administration of treatment,
- Patient decides to withdraw from the study, or

- General or specific changes in the patient's condition render the patient unacceptable for further treatment in the judgment of the investigator.
- Up to a total of 24 courses of therapy; about 2 to 3 years.

a. Patients who show no evidence of life-threatening infection or hemorrhage, or less than grade 2 clinically significant drug related non-hematologic toxicity (vomiting included) may be given a subsequent course at the same dose as the previous course. If clinically significant drug-related grade 2 toxicity is observed, the patient must have recovered to grade ≤ 1 before institution of the next course. If patients have clinically significant drug-related grade 3-4 non-hematologic toxicity, they may receive a subsequent course at one reduced dose level after resolution of toxicity to \leq grade 1.

b. Patients with a response (defined under section 10.0) and pre-course counts of granulocytes $>10^{9}/L$ and platelets $>50 \times 10^{9}/L$ who have sustained low counts of granulocytes $<0.5 \times 10^{9}/L$ or a platelet count $<30 \times 10^{9}/L$ for more than 2 consecutive weeks in the current cycle, may receive a subsequent course at 1 dose level reduction. A reduction of 2 dose levels may be considered if the myelosuppression was deemed severe and life threatening by the treating physician, and if it is in the patient's best interest.

c. Patients may receive further courses of therapy not earlier than 4 weeks from the previous course, provided the patient has recovered from myelosuppression considered to be related to chemotherapy. Patients with rapid increase in blasts may start additional therapy before 28 days from start of the previous course.

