8.0 Evaluations during the study

- **8.1** CBC, differential, platelet count 1-2 times weekly for 1st course, then every 2-4 weeks while on therapy. The frequency can be reduced to once per cycle after achieving CR or after sixth cycle (whichever first)
- **8.2** Creatinine, bilirubin, SGPT weekly for 1st course, then every 2-4 weeks while on therapy. The frequency can be reduced to once per cycle after achieving CR or after sixth cycle (whichever first)
- **8.3** Bone marrow aspiration to document remission then every 1-3 courses.
- **8.4** Cytogenetics at remission if abnormal pretherapy any time a bone marrow exam is performed. Omissions will not be considered as deviations.
- **8.5** Molecular testing depending on the positive tests pre-study (specific mutations, whole genome sequencing) any time a bone marrow exam is performed. Omissions will not be considered as deviations.
- **8.6** Multi-parameter flow cytometry for the presence of leukemia associated immunophenotype (minimal residual disease) any time a bone marrow exam is performed. Omissions will not be considered as deviations..
- 8.7 Blood samples (20-50cc) on days 1 (any time prior to first dose), 5 and 10 (+/- 3 days) of therapy (optional); marrow sample (2 cc) every 1-3 courses (optional). Samples are to be sent to [name] lab ([contact]). (Not all research samples may be collected at all time-points and omissions will not

be considered deviations.) Precourse samples may be obtained after day 27 of the preceding course, but prior to first dose of next course.

- **8.8** Blood sample (25-35cc) will be collected for assessment of immune function and effector cells at the time of remission, relapse, and about every 3 4 cycles. Samples are to be sent to [name] lab. (Not all samples may be collected at all times points and omissions will not be considered deviations.)
- **8.9** Peripheral blood specimens will be obtained at the time of complete remission and relapse, and evaluated for the presence of various T-cell subsets, NK cells and other immune effector measures

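### Duration of response is censored at an undefined last follow-up date, so responders who leave disease evaluation in remission may be credited with remission time nobody observed

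*Combined protocol and SAP*

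**What the plan says.** Duration of response (DoR) is part of the secondary objective in section 1.2: "Compare response durations, survivals and side effects of the two schedules". Section 11.5 starts it at confirmed CR or CRi, ends it at "the date of progression or death (whichever occurs first"), and adds: "DoR will be censored on the date of last follow-up". Time-to-event variables are estimated by Kaplan-Meier.

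The same section closes survival with the same term: "The OS is defined as the time period from the start of treatment till death or last follow-up whichever comes first". Last follow-up is defined nowhere in the document.

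The examinations that show continuing remission are in section 8.0. Item 8.3 reads "Bone marrow aspiration to document remission then every 1-3 courses". Items 8.1 and 8.2 schedule blood tests while on therapy and allow them to fall to once per cycle after CR. Under section 5.3(e), patients in CR or CRi "may be treated with additional courses of decitabine every 4-8 weeks or longer if approved by the PI". The same paragraph also says "Patients may be taken off study or treated on other programs (e.g. bone marrow transplantation"). Section 5.3 caps treatment as well: "Up to a total of 24 courses of therapy; about 2 to 3 years".

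No section links DoR censoring to a disease assessment, and none has a rule for missed assessments, transplant or new therapy.

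**The concern.** A contact that shows the patient is alive is the right closing date for survival. It is not enough for DoR, because knowing that someone is alive does not show that the marrow is still in remission. The schedule that would show this ends when the patient leaves treatment, and the plan allows responders to leave in remission.

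Take a hypothetical responder whose last remission marrow is at week 12, who then moves to another programme and is known to be alive at week 60. Read literally, section 11.5 gives this patient 60 relapse-free weeks, of which 60 − 12 = 48 were not observed. If the patient relapsed unseen and then died, the event is dated at death instead of relapse.

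At stake is a secondary comparison that section 2.4 makes part of the rationale, where the 10-day schedule is to be at least comparable on response duration.

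**Working it through.** The plan gives no DoR sample size, event count or expected median, so there is no figure to reproduce. The check has four steps.

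**1. Gap between assessments, from the plan's own figures.** A marrow every 1 to 3 courses, with courses 4 to 8 weeks apart, gives 1 × 4 = 4 weeks to 3 × 8 = 24 weeks between marrows, or longer with approved delays. Once a patient is off treatment, section 8.0 schedules no routine assessment.

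**2. Direction.** Let R be relapse, D death (D ≥ R), C last contact and S the last protocol assessment, all measured from response.

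- Under 11.5, a known relapse gives time min(R, C). An unknown relapse gives min(D, C).
- Since D ≥ R, min(D, C) − min(R, C) ≥ 0. A missed relapse can only lengthen the recorded time.
- If every relapse is captured, or C always coincides with a disease assessment, the excess is zero.
- Censoring leavers at S gives time min(R, S, C), with an event only if R ≤ min(S, C).

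**3. Size, by illustration.** Only the 45-week and 23-week medians come from the document (section 2.3, CR duration in a mixed AML/MDS cohort with chromosome 5 and 7 abnormalities). Everything else here is assumed: exponential times, the share and timing of departures, the reporting of later relapses, and survival after relapse.

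*Setting A:* true median 45 weeks, 26 weeks median from relapse to death, departure at weeks 4 to 40, last contact at weeks 26 to 130. Kaplan-Meier median DoR in weeks:

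| Responders leaving | 11.5 as written, no later relapse reported | Leavers censored at last protocol assessment |
|---|---|---|
| 10% | 47 | 45 |
| 20% | 50 | 45 |
| 30% | 52 | 45 |
| 40% | 55 | 45 |

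If half of later relapses are reported, the as-written medians are 46 to 49 weeks over the same range. If relapse to death takes 13 weeks instead of 26, with none reported, they are 46.6 to 51.5.

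*Setting B:* departure at weeks 0 to 52, last contact at weeks 52 to 156, relapse to death 13 or 26 weeks, no later relapse reported.

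| True median (simulated) | Leaving | 11.5 as written | Last assessment, later deaths still events | Last protocol assessment regardless |
|---|---|---|---|---|
| 45 (44.8) | 10% | 46.0–46.6 | 45.0–45.2 | 44.8 |
| 45 (44.8) | 30% | 48.7–50.6 | 45.5–46.1 | 44.8 |
| 45 (44.8) | 50% | 51.8–56.1 | 45.9–47.2 | 44.8 |
| 23 (22.9) | 30% | 24.3–24.6 | 23.9–24.0 | 22.9 |

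With nobody leaving, the rules agree.

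**4. Which departures count.** Twenty-four courses at 4 to 8 weeks take 24 × 4 = 96 to 24 × 8 = 192 weeks, well past a 45-week median. Simulated departures at weeks 96 to 192 leave the median at 45 under both rules. Only earlier exits matter: transplant, other programmes or withdrawal.

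**The case against.** The strongest reply is that last follow-up may simply mean the last evaluation of the patient. Sections 8.8 and 8.9 plan samples at relapse, and section 11.2 stresses timely recording of follow-up times and events. On that reading the two rules coincide. This stands as a possibility, but the plan does not say it, and the shared wording with overall survival points at least as much to a contact date.

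A reader might go further and infer that only survival contact remains once a responder leaves, so that DoR is certainly inflated. The documents do not support that: they describe no off-study follow-up of any kind. A reader might also infer that the comparison is tilted towards one schedule. With 10% leaving one arm and 40% the other, Setting A would show about 47 against 55 weeks in equal arms. But the plan gives no departure rate by arm, and both arms share the section 8.0 schedule.

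The effect is also small against chance. A 30% response rate in 100 patients gives 30 responders, about 15 per arm if split equally. Under Setting A with no departures, the difference in medians between equal arms has a standard deviation of about 26 weeks and exceeds 8 weeks in about 70% of trials. That limits the practical importance, but it does not justify a rule that leans one way.

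Finally, the alternative is not assumption-free. If the relapse hazard halves after leaving and 40% leave, the true median is about 51 weeks. Censoring at the last assessment still gives 45, while the present rule gives about 55 (half of relapses reported) to 59 (none). Neither rule is best in every case, so both should be reported.

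**Conclusion.** The point holds as a weakness in definition. Because 11.5 closes DoR on an undefined date shared with survival, a responder known only to be alive may be credited with unobserved remission time. The direction is upward whenever later relapses are missed.

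The size is not in the documents. Under the stated assumptions a 45-week median rises by about 2 weeks (10% leaving) to 10 weeks (40% leaving) if no later relapse is reported, and by about 1 to 4 weeks if half are. It rises by nothing if all are captured. The 24-course cap does not contribute materially to the median.

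The primary response rate, arm selection and stopping rules in 11.3 and 11.4 do not use DoR and are unaffected. The change is worth making because it is cheap, not because a conclusion of the trial depends on it.

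**What to change.** Replace the censoring sentence in 11.5 with:

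> Responders without progression or death are censored at the date of the last disease assessment (marrow, or blood counts with no evidence of relapse) that documents continued remission. Progression or death while under protocol evaluation is an event. Responders who leave protocol evaluation in remission are censored at their last protocol assessment, whatever is learned later.

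Report the present definition (last follow-up, with all known relapses and deaths as events) as a sensitivity analysis.

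The final clause matters. Censoring leavers at the last assessment unless a relapse is documented would make censoring depend on outcome. In Setting A with 40% leaving, it pulls the median down to 42.6 weeks if half of later relapses are reported and 40.7 if all are.

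The cost is a short change to 11.5, using assessment dates already collected, with no effect on treatment, randomization or sample size. The downsides are slightly fewer events, a wider interval, and off-protocol deaths not counted in the main DoR analysis. The rule also assumes that leaving is unrelated to relapse risk, which the sensitivity analysis checks. Section 9.0 does not define progression or relapse, and a definition should be added at the same time so that the event is as clear as the censoring.
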